### 8.2. Definitions

Term	Definition
Adverse Event (AE)	Any untoward medical occurrence in a patient or study subject
Serious Adverse Event (SAE)	
A serious event is any untoward medical occurrence that:
 
 
Results in death
 
Is life-threatening
 
Requires inpatient hospitalisation or prolongation of existing hospitalisation
 
Results in persistent or significant disability/incapacity
 
Consists of a congenital anomaly or birth defect
 
 
Other 'important medical events' may also be considered serious if they jeopardise the subject or require an intervention to prevent one of the above consequences.

The medical monitor will decide whether an AE is serious in other situations. Important AEs that are not immediately life-threatening or do not result in death or hospitalisation but may jeopardise the subject or may require intervention to prevent one of the other outcomes listed in the definition above, should also be considered serious.

### 8.3. Adverse Events

Volunteers will be monitored throughout the duration of the tests by investigational staff for any adverse events. A certified first aider (American Red Cross Adult First Aid/CPR/AED certified, or

equivalent) will be present during the training and test days should any subject require emergency first aid on-site. If any adverse events related to mosquito bites or the repellent product are apparent at any time during the trial, testing will stop immediately and details of how to access treatment, and how treatment will be paid for will be offered. Volunteers can only participate in a test a minimum of 72 hours after the screening bite test and subjects with known allergies to any of the product ingredients will not be eligible to take part.

Within 72 hours after laboratory testing an email will be sent to subjects asking them to report any adverse events that might have occurred since the end of testing. Adverse events that occur >72 hours after the end of participation in the trial will be passively monitored. An adverse event which is ongoing at the time of subject withdrawal or completion will be followed up until it resolves or until 30 days after the subject terminates from the study, whichever comes first.

#### **8.4. Compensation Due to Adverse Events**

If a subject is injured or becomes ill as a direct results of his or her participation in this study, the Sponsor will pay for all reasonable and necessary medical expenses required to treat the injury, as long as:

1. The injury or illness occurs during the subject's participation in the study, and
2. The injury or illness results directly from the test substance or study-related procedures.

If an insect tests positive for a pathogen, then the subject that this mosquito was aspirated from will be contact and informed of the result and advised to consult with a medical practitioner. All other subjects will be notified of the result and recommended to seek medical assistance if they feel ill.

The Sponsor, Medical Monitor, and Study Director will determine whether the injury is related to the subject's participation in the study. To do this, they may request to consult with the person/facility that provided medical treatment following an adverse event, which could require the subject's consent.

No additional compensation for adverse events beyond payments for medical expenses related to participation in the study is routinely offered. The Study Director and others involved in this study may be LSU employees. As employees of the University, they are protected under State Law, which limits financial recovery for negligence.

#### **8.5. Safety Reporting Procedures**

All adverse events and serious adverse events should be reported. Depending on the nature of the event the reporting procedures listed below should be followed. Any questions concerning adverse event reporting should be directed to the chief investigator in the first instance.

All adverse events should be recorded on the Adverse Event Record Form (Appendix 5) and Adverse Event Monitoring Questionnaire (Appendix 6) and entered into a log. All data should be kept securely and to maintain confidentiality. All adverse events will be reported to the sponsor, Livful Inc. Depending on the nature of the event the reporting procedures below should be followed, see Appendix 7.

Regardless of the relation of the adverse event to study participation, the event must be reported as a serious adverse event if it meets any of the definitions in section 7.2. AE questionnaires meeting the SAE definition will be submitted to the medical monitor within 24 hours. SAEs that are assessed by the Study Director as being both related and unexpected must be reported to the LSU IRB within 15 days of the Study Director becoming aware of the event.

In the case of a severe reaction such as anaphylaxis, it will be treated as an emergency and an ambulance will be called immediately by dialling 911 directly from a mobile. In addition, a trained First Aider will be called.

### **8.6. Risk Assessment**

The Study Director has determined this study to be “low-risk” when the hazards associated with trial design, randomization system and outcome measures, participating sites, study population, test product, trial supplied, data management systems, potential for adverse reactions, and oversight mechanisms are assessed. Day-to-day monitoring will be carried out at the study centre by a member of the study team with delegated responsibility.

Safety information regarding the repellent used in the trial have been assessed, material safety data sheets (MSDS) and labels have been read to be sure they are safe for human use. The active ingredient in the test product is IR3535. Subjects will be given an information sheet explaining the details of the ingredients and what to do if they have a reaction to the product or mosquito bites after completion of the test.

### **8.7. Data Management**

Informed consent forms will contain the subjects' full names. The subjects' names will be entered onto an enrollment log and each subject will be assigned a subject identification number. All other data collection forms will use the subject identification number only (see Appendix 8).

During screening the subject will self-complete an eligibility questionnaire including their date of birth and some medical history. All other data collected will be recorded in the case report form (CRF) and signed on each page by the researcher responsible. The CRF is considered to be source data. Data to be collected on the CRF are: subject number a date of test on every page, confirmation of informed consent, eligibility details, attractiveness test data (number of mosquitos attracted to arm); training data (successful attempts to capture mosquitos); leg measurements; test visit data (product application details, mosquitos caught, times of testing); and adverse event monitoring.

Raw data from the CRF will be entered into a database, from which datasets can be extracted for analysis. This database and any datasheets or analysis produced will be saved in a location with access limited by password identification to members of the study team. Data will be double entered and verified to ensure accuracy. The Study Director will confirm that all data from all subjects have been entered to avoid analysing an incomplete data set. CRFs will be kept in secure storage after completion. Information in the database will be linked to a relevant SOP, risk assessment, contract, and files of statistical analysis and location of study report.

## 9. Ethics and Dissemination

### 9.1. Research Ethics Approval

This study will be conducted in accordance with the EPA's final regulation at 40 CFR 26 that establishes requirement for the protection of subjects in human research. The protocol, informed consent form, and other required documentation must be submitted to an independent Institutional Review Board (IRB) and submitted to the EPA as required by 40 CFR 26.1125. These documents must be approved before any portion of the study is initiated, including recruitment of the subjects. To maintain scientific integrity in regards to testing procedure and clarity of the protocol, any revisions made to the protocol as a result of the protocol review process will be reflected directly in the protocol itself.

The report of the completed research is subject to the requirements at 40 CFR 26.1303 to provide documentation related to ethical conduct of the study.

The IRB responsible for approval and continuing review of this research is:

[name], IRB Coordinator  
[name]  
Louisiana State University  
Baton Rouge  
[name]

### 9.2. Protocol Amendments

All amendments and deviations will be reported to the study sponsor in a timely manner. All amendments and deviations to the protocol will be reported to the IRB consistent with their standard reporting guidance. Protocol amendments may not be initiated without prior IRB review and approval except where necessary to eliminate apparent immediate hazards to human subjects.

All amendments, deviations, and any adverse events will be documented in the final study and reported consistent with Good Laboratory Practices (GLP) 40 CFR 26, Subpart K, and IRB reporting procedures. Documentation will include a description of the change, the reason for the change, the effect of the change on the conduct and outcome of the study, and whether or not the IRB approved each amendment prior to implementation.

### 9.3. Consent

Consent to enter the study must be sought from each volunteer only after a full explanation has been given, an information leaflet offered and time allowed for consideration. Signed volunteer consent must be obtained. The right of the subject to refuse to participate without giving reasons must be respected. Subjects must be informed of their right to withdraw from participation at any point in the study without forfeiting benefits to which they are entitled.

### 9.4. Confidentiality

Subjects' identification data will be required for the enrollment process. This data will be linked on a single form (subject enrollment log) to their unique identification number. The subject identification number will be used on all other data collection forms, which will not contain any other identifiable

data. The subjects' names will not appear anywhere on the data sheet, or in the reports. The Test Facility will preserve the confidentiality of subjects taking part in the study.

The information obtained from subjects taking part in this study will be used by the researchers, and the Sponsor/Funder, and will become part of the report. All reports (as well as all study-related records) will be kept as confidential as possible under US and State law. The results of the study are not intended for publication; however, if any of the study-related data are published, subjects' identities will remain confidential.

All efforts will be taken to maintain the confidentiality of the pregnancy test results. The test results will not be recorded, and will not be disclosed to anyone other than the test subject, the verifying employee, and/or the Study Director.

The study records will be maintained at the Test Facility in locked cabinets, and electronic files kept on a password protected computer server. No one outside researchers, Sponsor, IRB, or certain governmental agencies will have access to subjects' personal information.

## **9.5. Record Retention**

Data and all appropriate documentation will be stored for a minimum of 10 years after the completion of the study, including the follow-up period.

## **9.6. Payment for Participation**

Subjects will be paid to compensate for their time when participating in testing. Subjects will be paid \$10 each for the consent and enrollment appointment, estimated to take around 1 hour, regardless of whether they choose to enroll in the study. Subjects will be paid \$40 each for taking part in training, estimated to take approximately 2 hours, regardless of whether they continue their enrollment in the study. For the field test, subjects will be paid \$10 per hour for taking part in the field test, for the first 8 hours, and \$15 per hour for participation beyond the first 8 hours. These payments will be rounded up to the next hour. If field test days are truncated, such as due to bad weather, payments will be made per hour.

An alternate who shows up to the test site and who is not needed to replace a test subject will be paid \$20. The decision as to whether an alternate is needed will occur within the first two hours of the test, before all the treatments have been finished, at which point they can leave. If an alternate is asked to replace a subject, he or she will be paid at the same rate as other test subjects, as described above.

All payments will be made in cash or pre-paid card in person at the end of each event.

The Study Director, or other delegated staff may end a particular subject's participation on a test day at any time (see section 4.4). If the Study Director or other delegated staff ask a subject to withdraw from the test and they have complied with all of their requests, or if a test subject needs to withdraw early because of a health or emergency reason, full payment will still be made even if the test subject has participated for less than the full test day. This will not affect payment for any previous test days that have been completed.

If a subject is asked to withdraw from the test because they have not followed all the directions, or if they choose to withdraw from testing early on a test day for a non-health related or non-emergency reason, full payment will not be made if the test subject participates in less than the full test day. Instead, they will be paid for the number of hours (rounded to the nearest hour) at a rate of \$10 per hour (\$15 per hour beyond the first 8 hours). This will not affect payment for any previous test days that have been completed.

Subjects that have reached treatment failure and are no longer part of the testing, but who are unable to leave the test site as they are reliant on trial staff for transport will be paid until they are transported back to the Test Facility.

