
SARS-CoV-2 infection
	
The study will comply with all federal, state, and local restrictions and guidance related to COVID-19 in effect at the time of the study.
 
The Study Director or delegated person will conduct phone screening for symptoms of COVID-19 1-2 days prior to the mosquito attractiveness assessment and training visit, and the test day visits.
 
Appropriate PPE and handwashing supplies will be made available for all study personnel and subjects, and cleaning supplies will be available to disinfect surfaces after subject encounters.
 
Staff will also be monitored for signs, symptoms and exposure to COVID-19 to reduce study subject exposure to sick individuals.
 
Individuals over 55 will be excluded from the study as they are more vulnerable to the effects of SARS-CoV-2 infection.

Irritation of the eyes or respiratory tract from exposure to IR3535
	
During handling and application of the repellent, eye protection will be worn by the handler. Subjects will wear eye protection during application only. Application and handling will be carried out in a well ventilated area.

Allergy from exposure to IR3535
	
Volunteers will be excluded if they have a known allergy or sensitivity to any of the product ingredients or any insect repellent products, or any skin condition that may affect their reaction to the product.

Fatigue from long test day.
	
Subjects will be provided with breaks as needed between the test periods. Subjects will have an opportunity to eat meals and snacks, stretch and walk around, and will have opportunities to use the restroom as necessary.
 
Where a subject enrolls to participate in more than one test day, at least 72 hours will lapse between each test day to allow subjects to rest and recover.

Risks associated with being outside in a hot humid climate e.g. sunburn, heat stroke.
	
Water and other drinks will be provided to prevent dehydration and snacks will be provided to maintain blood sugar levels if necessary. Subjects will be told at the consent meeting and reminded at the training to bring snacks, lunch/dinner, and entertainment to occupy their time during breaks between test periods. A cooler will be available to store meals and snacks brought by subjects.

---

---

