If an individual still wishes to enroll in the study, he or she will be asked a number of questions to ensure they have fully understood the information given. These questions are given in the **Table 2** below. Only if the subject can demonstrate their comprehension of the study procedures, will they then be asked to sign the Informed Consent Form (ICF), which will be posted or emailed in to the Study Director. If the signed ICF is emailed, the subject will be asked to bring the original to their first in-person session, whereupon they will be given a photocopy. The Test Facility will retain the original of the ICF.

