**Table 2. Questions posed to subjects to confirm understanding of study procedures and examples of acceptable responses.**

Questions	Examples of acceptable responses
What part of your body will be treated?	Lower leg
What product will be used in this study?	IR3535, insect repellent
What will you be wearing during the exposure period?	Long pants, long-sleeved shirt, gloves, head net
How long will you be exposed to mosquitos for during the field test for each exposure?	5 minutes every 30 minutes
What are the potential discomforts or hazards from this study?	Exposure to mosquitos, being outside in hot weather,
Do you have the freedom to quit or withdraw from the study at any time?	Yes

---

If you quit or withdraw from the study, for how many hours will you be paid?
	
For the duration of my participation, or for 14 hours if I withdraw on a test day for a medical /emergency reason

---	--

---

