### Subject Arrival

Subjects will be asked to arrive at the Test Facility at a specific time, 3-4 hours prior to the start of testing. This will allow time for registration, randomization and treatment before travel to the test site. The subjects will have a briefing and a compliance check. Subjects will be reminded that they are free to withdraw at any time and that they will be compensated for their participation up to the time of their withdrawal. They will also be reminded that they have the option to request that their data not be used.

Test subjects will be reminded not to engage in activities that could promote sweating and abrade the treated leg (e.g., rolling down pants, crossing legs), and to be careful when using the restroom to protect the treated leg.

Due to COVID-19, all study staff and subjects in attendance on test days will wear masks and where possible maintain 6 feet of social distancing. Masks may be removed during exposure periods to allow subjects to aspirate mosquitos. Staff and subjects will be required to have their temperature tested using an infrared thermometer. Subjects who fail to abide by social distancing and mask wearing provisions will be asked to leave and may be replaced.

A study staff member will orally verify each subject's compliance with the pre-test conditions on each test day prior to performing any treatment with a test substance. They will additionally check that eligibility criteria have not changed for example any new health conditions that may affect participation.

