All insects landing on the treated and control subjects' exposed lower legs will be collected by aspiration (before they have chance to probe or bite) and labelled with the subject number, treatment status, date and time of collection. Mosquitos will be identified to genus or species as appropriate. Then samples will be pooled by subject and date and tested for pathogen prevalence as appropriate. Mosquitos landing elsewhere on the body will not be collected.

Human landing collections for each subject will continue until treatment failure. Treatment failure is defined as one mosquito landing followed by a confirmatory landing either in the same 5 minute exposure period, or in the following exposure period. If treatment failure is reached in more than half of subjects, all other subjects will also stop testing and the test will be concluded. If treatment failure is not reached in more than half of subjects, the test will continue until 14 hours post application for the lotion, or 13 hours for the wipe. A median CPT can be established when there is time to treatment failure data for half the subjects, so at this point there is no need to risk exposure of subjects who have not reached treatment failure.

Between exposure periods all subjects will have access to restroom facilities, and a shaded, screened location with adequate seating. In addition, subjects will have access to cold drinks (water, soft drinks, etc.) and snacks to keep them hydrated and to maintain their blood sugar. Subjects may also consume their own food or drinks they bring; read, or engage in other leisure activities. Test subjects will be reminded not to engage in activities that could abrade the treated leg and to be careful when using the restroom to protect the treated leg.

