## 7. Statistics and Data Analysis

### 7.1. Sample Size Calculation

EPA statisticians used a Weibull distribution to simulate the sample size required to estimate the median CPT to a given degree of precision. A power analysis of these outputs resulted in a sample size of 13 subjects being chosen. This number allows for over 90% power at a range of expected median CPTs from 2-8 hours (Appendix 4: Sample size calculation).

This sample size is appropriate to achieve at least 90% power that the ratio of 95% LCL mCPT/mCPT  $\geq$  0.6), given that the P5MR (i.e., CPT5th percentile/mCPT) is assumed to be equal or greater than 0.5. The assumption for the variation of CPT data distribution is characterized by the value of P5MR, associated with the selected sample size and the result of power. The P5MR value characterizes the spread of the CPT data distribution. For two products with same mCPT, the product with lower value of P5MR has a wider range of CPT data.

To maintain gender balance among the volunteers, at least 6 volunteers of each sex will be recruited to test each product. An additional 2 subjects will be required to act as untreated controls. Five alternate subjects will be invited to take part in each study day. Subjects will be able to take part in one or both test days. Therefore, a minimum of 20, and a maximum of 40 subjects will be required to complete the trial.

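### The test-day pay reminder omits the full-payment exception for health and emergency withdrawals, and Table 2's single 14-hour figure cannot equal the full day of both products

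*Protocol*

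**What the plan says.** The protocol describes pay on early withdrawal in three places.

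- **Section 9.6, Payment for Participation.** Field-test pay is $10 an hour for the first 8 hours and $15 an hour after that. If a subject has to leave early for health or an emergency, or has complied with all requests and is asked by staff to withdraw, "full payment will still be made even if the test subject has participated for less than the full test day". Subjects who leave for other reasons, or who did not follow directions, are paid for the hours attended. No hours or dollar amount is attached to full payment.
- **Section 4.2, Table 2.** The acceptable answer on pay after withdrawal is the duration of participation, "or for 14 hours if I withdraw on a test day for a medical" or emergency reason. Section 4.2 makes comprehension a gateway to consent: "Only if the subject can demonstrate their comprehension of the study procedures, will they then be asked to sign the Informed Consent Form".
- **Section 6.7, Subject Arrival.** In the test-day briefing, subjects are reminded that they may withdraw at any time and that "they will be compensated for their participation up to the time of their withdrawal". No exception follows.

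On the length of the day, Section 6.7 (Human Landing Catches) says that, unless more than half of the subjects have failed, "the test will continue until 14 hours post application for the lotion, or 13 hours for the wipe".

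**The concern.** The reminder is the last statement about pay that a subject hears before a long day outdoors. Table 1 lists fatigue from the long day and, separately, "Risks associated with being outside in a hot humid climate e.g. sunburn, heat stroke" among the hazards. Section 9.6 removes the financial reason for an unwell subject to stay on. A reminder that mentions only pay up to the time of leaving can put that reason back. It also omits the compliant subject whom staff ask to withdraw, to whom Section 9.6 likewise gives full payment.

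The second matter is smaller. Table 2 is used to decide whether a volunteer has understood the study well enough to sign, so its model answer should be right for both products. It gives the same number of hours for test days of different maximum length.

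What is at stake is accurate information to subjects. Neither matter touches the endpoint, the sample size or the Kaplan-Meier analysis.

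**Working it through.** **Inputs.** Hourly rates and rounding up to the next hour: Section 9.6. The 14 hours: Table 2. Caps of 14 hours (lotion) and 13 hours (wipe) after application: Section 6.7. The times of withdrawal below are assumed, for illustration. They are whole paid hours, so that rounding plays no part.

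**Pay formula.** For h paid hours, Pay(h) = 10 × min(h, 8) + 15 × max(h − 8, 0).

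**Step 1: reminder against Table 2, health or emergency withdrawal.** Table 2 gives Pay(14) = 10 × 8 + 15 × 6 = $170, whenever the subject leaves.

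| Leaves after (paid hours) | Reminder, as worded | Table 2 | Gap |
|---|---|---|---|
| 3 | 10 × 3 = $30 | $170 | $140 |
| 8 | 10 × 8 = $80 | $170 | $90 |
| 13 | 10 × 8 + 15 × 5 = $155 | $170 | $15 |

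Section 9.6 states no amount, so it has no dollar column. Its rule is nevertheless plain: this subject is not paid by hours attended. The reminder, as worded, pays by hours attended. The conflict is therefore between the reminder on one side and Section 9.6 with Table 2 on the other.

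**Step 2: one figure for two products.** Let c be the difference between the moment paid time starts and the moment of application, plus any time paid after the cap. The maximum paid day is 14 + c hours for the lotion and 13 + c for the wipe. For 14 hours to be the full day of both, c would have to be 0 and 1 at once. Rounding up does not help, because the two lengths differ by exactly one hour and still do so once both are rounded up. At this length the extra hour is paid at $15, for example Pay(14) − Pay(13) = 170 − 155 = $15.

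**Step 3: which product the 14 hours fits.** This cannot be settled. Appendix 3 lists an exposure at 14 hours, and 13 hours also appears on its grid. Each exposure lasts 5 minutes. Counted from application to the end of that exposure and rounded up, the days become 15 hours (10 × 8 + 15 × 7 = $185) and 14 hours ($170). Counted to the nominal cap, they are 14 hours ($170) and 13 hours ($155). Only the one-hour mismatch survives every reading.

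**The case against.** The reminder can fairly be read as the general rule. It is attached to the freedom to withdraw at any time, it does not say that pay stops for illness, and it agrees with Section 9.6 for non-health withdrawals and with the first half of the Table 2 answer. Subjects have also been questioned on the medical exception at consent. This lowers the risk of misunderstanding and is a reason to call the point minor. It does not make the reminder correct: the sentence covers all withdrawals, and the exception is missing on the day it would be used.

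A reader might go further and infer that the protocol sets three different payments. It does not show that. Table 2 and Section 9.6 share one principle, and Table 2's 14 hours can be read as the amount that Section 9.6 leaves unstated.

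A reader might also infer that Table 2 pays an unwell subject more than one who stays, because "If treatment failure is reached in more than half of subjects, all other subjects will also stop testing and the test will be concluded". That requires full payment to mean the actual length of the day, which the protocol nowhere says. Section 9.6 pays truncated days by the hour, which could point that way; a fixed 14 hours in Table 2 points the other way. Putting a dollar figure on that reading would measure an assumption.

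Finally, Table 2 offers examples of acceptable answers and is not the pay schedule. The information sheet and consent form (Appendix 2) are provided separately, are not available here, and may state the amount. That could settle what full payment means. It would not repair the wording of the reminder.

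**Conclusion.** The point holds in limited form and is minor. First, the Subject Arrival reminder conflicts with Section 9.6 and Table 2 for health and emergency withdrawals, and with Section 9.6 for compliant subjects asked to leave. Against Table 2 the gap is $140 for a subject leaving after 3 paid hours, and it shrinks the later the subject leaves. Second, Table 2's 14 hours cannot be the full day of both the lotion and the wipe, a mismatch of one hour or $15 if full payment means the maximum day.

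The first part rests on the reminder being given as written. The second needs only the two caps in Section 6.7. If full payment is meant as a flat 14 hours for either product, the second part becomes a matter of saying so in Section 9.6. No effect on Complete Protection Time is claimed.

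**What to change.** 1. In Section 6.7, Subject Arrival, add to the reminder the Section 9.6 exception for health, emergency and staff-requested withdrawal of a compliant subject.
2. Make the Table 2 answer and Section 9.6 agree. Either word the Table 2 answer to follow Section 9.6, by product if the maximum day is meant, or state in Section 9.6 that full payment is a flat 14 hours.
3. Check that the information sheet says the same.

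The sponsor and the IRB choose the rule; the passages need only state the same one. The cost is one sentence in Section 6.7, one Table 2 cell or one sentence in Section 9.6, and any matching wording in the information sheet, with IRB review. Staffing, exposure schedule, sample size and analysis are unchanged.
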